### **15. SUBJECT WITHDRAWALS**

Subjects will be advised during the consent process that they have the right to withdraw from the study at any time without prejudice. They can choose to use the website as much as they want (or not at all). We are interested in obtaining survey data as well as feedback about the user experience from as many participants as possible, including those who chose not to use the website or found it hard to navigate. This information is useful in identifying ways to improve the website and facilitate user engagement.

Subjects will not be withdrawn without their consent unless they meet the criteria outlined in the Fraudulent Participant Protocol (see uploaded). Subjects who are withdrawn under this protocol will be replaced and will not count toward final enrollment numbers. Subjects can choose not to complete any or all of the study assessments. They can also completely withdraw from the study with no future contact if they choose. In this case, any data they have previously provided may be used in analyses.

### **16. PRIVACY AND CONFIDENTIALITY OF SUBJECTS AND RESEARCH DATA**

All data will be used solely for research purposes and will be securely locked in designated file cabinets, URMC managed Box folder dedicated to project, Project REDCap database, and an encrypted, HIPAA-compliant Cloud database (Azure; for data collected via the website; see above). Identifying information will be stored separately from other data, which will be stored by research ID number. Multiple procedures will be implemented to protect participant data collected through the website, which are further detailed in the section “Protections Against Risks” and Data Security Assessment form. Only senior key personnel and project research staff will have access to the data.

The following table summarizes the project data flow. MHFC IT will set up and manage permissions for URMC Project Box folder. Only project staff will have access to REDCap and Box folders.

Data Element	How Data Collected	Where Data is Stored	How Data is Managed
Information Sheet,	REDCap	REDCap,	MHFC IT; Project Staff

Screening Survey, Contact Information		Back-ups URMC Box	
Baseline (T1) Surveys, Timepoint 2 surveys, Timepoint 3 surveys	REDCap	REDCap, Back-ups URMC Box	MHFC IT; Project Staff
Follow-up Interview	Zoom	URMC Box	MHFC IT; Project Staff; Audio/video data is transcribed verbatim; audio/videos deleted once transcript verified
FMF Connect Teacher Companion website usage data and User's inserted data	Website and Azure services	URMC-managed account on Azure	Access is restricted to authorized individuals and every access to the data will be logged, data is encrypted in transit and at rest. Azure account is set up in compliance with UR/URMC policies and monitored by ISD.

## 15. DATA / SAMPLE STORAGE FOR FUTURE USE

All data (de-identified and identifying) will be securely stored locally for an indefinite period. De-identified and identifying information will be stored separately as detailed above. Novel research questions may arise in the future that this important dataset could answer. Retaining identifying information would facilitate contacting individuals (subsequent to new IRB approval) to see if they would be interested in participating in follow-up research. MHFC has well-established data security procedures in place for long-term storage and maintenance of data. Only approved project staff will have access to data.

## 16. DATA AND SAFETY MONITORING PLAN

Because the research involves the provision of a website-based intervention for teachers, the risk for a serious adverse event due to provision of the intervention is low. Adverse events that could occur include adverse events in the classroom involving students with FASD such as aggression or violence towards others, maltreatment, self-harm or suicidality, or threats of violence to others or to the school. However, these occurrences are unlikely to be a direct consequence of participation in the proposed research or intervention.

[name] will assume ultimate responsibility for the safety and well-being of research participants and the integrity of data collected. [name] has conducted several RCTs on interventions for caregivers of children with FASD. She is a licensed psychologist in the state of New York and is involved in other clinical and research activities at MHFC where maltreatment and suicidality are commonly reported.

The well-being of participants will be monitored throughout the course of the proposed research. If there are concerns regarding a participant during interactions with research staff, staff will immediately contact [name] for consultation and a plan will be developed to address the concerns raised. Additionally, because MHFC provides other treatment programs, there are other back-up clinical supervisors available for consultation for

immediate needs. A phone tree will be established, similar to other projects at MHFC, and will be provided to research staff. [name] will meet with research staff at least weekly to provide supervision and will assess participant well-being. [name] will consult with other co-Investigators and clinical staff at MHFC, as appropriate, to address participant well-being concerns.

The IRB will be notified immediately of any adverse events via telephone and submission of a “University of Rochester Serious Adverse Event Report”. Such events would also be reported to NICHD. Ethically, we are committed to ensuring the welfare of participants. Any significant mental health or safety issues detected during the conduct of this investigation will be discussed with participants and options for the receipt of services presented.

## 17. DATA ANALYSIS PLAN

Qualitative Interview Data: Data will be analyzed thematically to understand users' experiences with the FMF Connect Teacher Companion website and research trial. Thematic analysis focuses on identifying patterns or themes within the data. Consistent with the approach advocated by Miles, Huberman, and Saldana (2014), research team members will first familiarize themselves with the data, iteratively reviewing each transcript, and independently assigning initial codes (“first-level coding”). The team will then come together and discuss, operationalize, and refine each code. We will then generate “second-level codes” which consider categories or deeper meanings among first-level codes. During this process we will examine interrelationships and networks among codes and build a preliminary thematic framework. Transcripts will then be recoded and codes refined through further discussion and consensus, as needed. Participant and group “fit” with the framework will also be assessed, with confirmatory and disconfirmatory evidence for the model examined. Participant matrices may also be utilized to examine variance in themes across participants and key demographic factors, pre-post intervention change, or usage patterns. Interviews will be coded using qualitative content analysis.

Quantitative Data Analyses: Quantitative analyses will be largely descriptive, as appropriate for pilot trials (Lancaster et al., 2004) and will include effect sizes and 95% confidence intervals of the following measures in the assessment battery:

- FASD Knowledge survey
- Attributions and Behavioral Strategies
- Perceived Self-Efficacy (TSES)
- Study Design Feasibility and Acceptability (SES)
- Program Satisfaction (uMARS)

The below table summarizes how each analysis will address each sub-aim of the current study.

Aim	Evaluated Using
Intervention Feasibility	
• technological functionality	uMARS means/standard deviations; website crash reports; user experience interviews

• acceptability of website	uMARS means/standard deviations; user experience interviews
• typical usage patterns	Website usage data, including frequency, length, and timing of use
Study Design Acceptability	
• enrollment and attrition rates	N consented; N with complete data; rate of attrition
• acceptability of randomization and control condition	SES means/standard deviations; user experience interviews
• assessment acceptability and sensitivity	Rate of assessment completion; pre-post effect sizes and 95% confidence intervals
• optimal intervention length	Website usage patterns
• predictors of attrition	Rate of attrition; demographic and baseline variables

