#### **4. STUDY DESIGN**

The study design is a 2-parallel arm, staggered design pilot RCT. All subjects will complete baseline assessments. Then they will be randomly assigned to either Group 1) Website, or Group 2) Delayed treatment control. Group 1 will receive access to the website immediately. After six weeks, both groups will complete Timepoint 2 assessments. Selected participants will complete a qualitative interview about their experience using the website. After completion of Timepoint 2 assessments, Group 2 will receive access to the website (Group 1 will retain access to the website). After an additional six weeks, both groups will complete Timepoint 3 assessments and the study will conclude.

Assessments will include measures of FASD knowledge, teacher self-efficacy, teacher attributions and behavioral strategies, and satisfaction with the technology and study. Website usage data will be collected using Azure Application Insights (feature that can be enabled on our URMC-managed Azure account). Participants will be assigned to groups using simple randomization using manual 50/50 chance randomization.

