#### **5. SUBJECT POPULATION**

The study population will be U.S. teachers of grades K-5. We will aim to enroll 90 participants to achieve a final sample size of 50, assuming a 45% attrition rate (consistent with recent 3-timepoint online studies in our lab). Additional participants will be enrolled if attrition is greater than anticipated.

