## **9. STUDY PROCEDURES**

After informed consent, participants will be asked to complete screening questions to assess for eligibility criteria. Subjects who are not eligible will be told immediately and the module will end. Subjects who are eligible will be randomized to either Group 1 (Website) or Group 2 (Delayed Treatment Control). Randomization will be completed using manual 50/50 chance randomization. After randomization, subjects will complete the remaining baseline surveys (see details on the assessment battery below).

Once baseline surveys are complete, subjects in Group 1 will receive immediate access to the website. After 6 weeks, all subjects will be re-contacted to complete timepoint 2 surveys. User implementation data will be gathered through the website. To further assess acceptability, satisfaction, and barriers and facilitators of website use, selected participants will complete qualitative interviews over HIPAA-compliant Zoom or telephone. Interviews will be recorded and later transcribed verbatim. Participants will be selected for interviews based on patterns of website usage, personal demographics such as race, ethnicity, job title, and years of experience, and school geographic setting. A total of 5 participants will be interviewed from Group 1 at Timepoint 2.

After completion of Timepoint 2 assessment, Group 2 will receive access to the website (Group 1 will retain access to the website). After another six weeks, all subjects will complete Timepoint 3 assessments. A total of 5 participants will be interviewed from Group 2 at Timepoint 3, selected using the same procedure as for Timepoint 2.

The study coordinator will email participants to the email they provided to inform them they have access to the website and alert them to their login information.

Participants will be prompted to complete surveys upon reaching each timepoint via automated

invitation sent to the email they provided in REDCap. If they do not complete the surveys within three days, they will be sent another email reminder. If they do not complete the surveys within a week after the first reminder, they will be called by the study coordinator.

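### Section 17 names only a pre-post contrast and does not specify the randomised Group 1 versus Group 2 comparison at Timepoint 2

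*Combined protocol and SAP*

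**What the plan says.** Section 17 describes the quantitative analysis as mainly descriptive and says that it "will include effect sizes and 95% confidence intervals of the following measures in the assessment battery". Five entries follow: FASD Knowledge, Attributions and Behavioral Strategies, self-efficacy (TSES), the Study Experiences Survey (SES) and program satisfaction (uMARS). No contrast, time point, group term or covariate is attached to them.

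The aim table in the same section names one contrast, in the row for assessment acceptability and sensitivity: "Rate of assessment completion; pre-post effect sizes and 95% confidence intervals". The only related wording is in the qualitative paragraph, which would compare themes across "key demographic factors, pre-post intervention change, or usage patterns". Neither place defines the interval by group.

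The design offers more than this. Section 4 describes two parallel randomised arms, both assessed at T2 after six weeks, and then: "After completion of Timepoint 2 assessments, Group 2 will receive access to the website". Section 9 says the study will measure a preliminary effect of the website on teacher outcomes, and section 2 says the pilot is to inform a future RCT.

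Sections 4 and 9 differ on the order of baseline and allocation. Section 4 says: "All subjects will complete baseline assessments. Then they will be randomly assigned". Section 9 says: "After randomization, subjects will complete the remaining baseline surveys".

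**The concern.** T2 is the only assessment after baseline at which one randomised group has had the website and the other has not. By T3 both have had it. A reader who follows section 17 as written would compute change within a group and would have no instruction to compare the groups at T2.

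Change within the exposed group mixes three things: any website effect, the effect of answering the same items again, and whatever shifts over six weeks of a school year. Section 17 does not define sensitivity. If it means responsiveness to the website, a measure that moves only through repetition or the passage of time would look sensitive. An effect size carried from this pilot into the planning of the future RCT would have the same fault.

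The named contrast also does not fit every listed measure. Some have no value before access, so a pre-post effect size cannot be formed for them.

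**Working it through.** **1. Which contrasts the schedule allows** (Study Assessment Battery, section 9)

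| Measure (items) | Collected at | Pre-access to post-access change | T2 group difference |
|---|---|---|---|
| FASD Knowledge (28), TSES (10), Behavioral Strategies (36) | Baseline, T2, T3 | Group 1: baseline to T2. Group 2: T2 to T3 | Yes, baseline-adjusted |
| Attributions, RCB (30) | T2, T3 | Group 1: none. Group 2: T2 to T3 | Yes, unadjusted only |
| SES (10) | T2 | None | Not a before-and-after measure of the website |
| uMARS (32) | T2 in Group 1; T3 in both | None | None; Group 2 has no T2 value |

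The missing RCB baseline is not a table-reading artefact, because the stated item totals confirm it:

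- Baseline: 39 + 28 + 10 + 36 + 3 = 116, as stated. With RCB it would be 146.
- T2, Group 1: 28 + 10 + 30 + 36 + 3 + 10 + 32 = 149, as stated.
- T2, Group 2: 149 − 32 = 117, as stated.
- T3: 28 + 10 + 30 + 36 + 3 + 32 = 139, as stated.

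Group 1 does have RCB at T2 and T3, but it has access throughout that interval. For attributions in Group 1, the T2 group difference is therefore the only website contrast available.

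**2. Sample size.** Section 5 aims for 90 enrolled and 50 final, "assuming a 45% attrition rate". Check: 50 / (1 − 0.45) = 90.9, and 90 × 0.55 = 49.5. The plan's figure reproduces to within rounding. Equal arms give 25 per arm at the end.

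**3. Bias under drift.** Let the website effect be E and the drift common to both arms be D, in SD units.

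- Pre-post change in Group 1 has expectation E + D.
- The T2 group difference has expectation (E + D) − D = E.

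If E = 0, pre-post returns D in full. If E = 0.4 and D = 0.2, pre-post returns 0.60 and the T2 difference 0.40. Simulation (20,000 trials, 25 per arm) agrees: with zero effect the pre-post mean equalled the drift and the adjusted T2 difference averaged 0.00. The documents give no drift, so these values only illustrate.

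**4. Precision.** With n per arm and an assumed baseline-to-follow-up correlation r = 0.6, the 95% half-widths in SD units are:

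- Pre-post, one arm: t(n−1) × √(2(1−r)/n)
- T2 difference, baseline-adjusted: t(2n−3) × √(2(1−r²)/n)
- T2 difference, unadjusted: t(2n−2) × √(2/n)

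| n per arm at T2 | Pre-post | T2 adjusted | T2 unadjusted |
|---|---|---|---|
| 25 (worst case: all 45% attrition by T2) | 0.37 | 0.46 | 0.57 |
| 33 (attrition even over the two intervals: 90 × √0.55 ≈ 67) | 0.32 | 0.39 | 0.49 |

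At n = 25 the adjusted half-width runs from 0.54 (r = 0.3) to 0.34 (r = 0.8), and pre-post from 0.49 to 0.26. Section 5 does not split attrition by time point, so both rows are assumptions.

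**5. Selective dropout.** One assumed scenario was simulated: 45 randomised per arm, zero effect, zero drift, r = 0.6, about 45% lost by T2 in each arm, and Group 1 retention tied to its T2 score (log-odds 0.5 per SD). The adjusted T2 difference was biased by about 0.14 SD and Group 1 pre-post by about 0.09 SD. Completion was 54.8% and 55.0% in the two arms, so equal completion rates would not reveal the problem.

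**The case against.** **The plan may intend a between-group effect size.** The general sentence in section 17 is broad enough to include one, and T2 data will exist in both arms. This stands. A reader might infer that the sponsor means to discard the randomised comparison; the text does not support that. The defect is that the contrast is not specified.

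**Pre-post need not mean Group 1 alone.** The aim table does not say so, and for three measures Group 2's unexposed change from baseline to T2 could be shown alongside. This also stands, and it makes the drift bias conditional on a Group 1-only reading. It does not help attributions, which have no baseline in either group.

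**This is a descriptive pilot.** A reader might go on to quote how often a pre-post interval would exclude zero with no website effect, as if that were a false-positive rate. The documents plan no hypothesis test, significance level or progression rule tied to such an interval, so that reading fails. What remains is a biased estimate. Being descriptive does not settle which difference is to be described.

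**The T2 difference is not always better.** Under outcome-related dropout in Group 1 only, with no drift, it can be the more biased of the two. This stands and limits the claim to drift common to both arms.

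**The order of baseline and randomisation is a separate matter.** Largely so. Under section 9 the baseline surveys still precede website access, so they remain pre-exposure values, and no section says when participants learn their allocation. It matters here only because baseline adjustment would use those scores.

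**Conclusion.** The point holds as a gap in specification. Pre-post is the only outcome contrast section 17 names, and no section specifies Group 1 versus Group 2 at T2, although the study says it will measure a preliminary effect. That the named contrast cannot be formed for attributions in Group 1, for SES or for uMARS follows from the assessment schedule and needs no assumption.

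The size of the bias does rest on an assumption. Within Group 1 alone it equals the retest or time drift, which the documents do not give. The consequence for assessment sensitivity also depends on reading that undefined term as responsiveness to the website.

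The plan should be changed, because the correction uses data already scheduled. It does not put the study's main purpose at risk: usage, acceptability, enrolment and attrition are assessed in other ways and are unaffected.

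**What to change.** In section 17, including the sensitivity row:

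1. Make the Group 1 minus Group 2 difference at T2, as randomised and regardless of website use, the main effect-size estimate, with a 95% confidence interval and no hypothesis test. Adjust for baseline for FASD Knowledge, TSES and Behavioral Strategies. Leave RCB unadjusted.
2. Keep pre-post change as secondary and descriptive. Define it as baseline to T2 in Group 1 and T2 to T3 in Group 2. Where a baseline exists, show Group 2's unexposed change from baseline to T2 beside Group 1's.
3. Keep SES and uMARS descriptive.
4. Reconcile sections 4 and 9 on whether the baseline surveys come before or after randomisation.
5. Report T2 completion by arm, and state that the T2 difference removes drift common to both arms but not bias from differential dropout.

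The cost is a few sentences in section 17, one reconciliation and a little more descriptive analysis, with no new data and no change to the enrolment target. The price in precision is the wider interval shown in the working.
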